3. METHODS

Description of Population and Sample

Our population consists of male and female youth aged 10-18 years that have been diagnosed with a concussion by a physician. Youth presenting to the David Braley Clinic, McMaster Children's Hospital, HWCDSB, Montreal Children's Hospital or physicians in the community will be randomly assigned to the intervention or control groups.

A clinically significant effect of 10% decrease in repeat head injury and 10% decrease in recovery time would be of interest. The sample size calculation was done using parameters with a two sided significance of 0.05 and a power of 0.8 and based on our primary outcome of repeat head injury which is a binomial variable. Our anticipated incidence rate was compared to two rates of incidence in clinical settings and in the literature:

- 16% rate common in the literature
- our anticipated 2% rate with adherence to protocols (from previous B2P study) N=128
- 37% rate from concussion clinic at MCH and
- 13% rate of our pilot data N=100.

The larger number will be sought (sample size takes into consideration 20% refusal rate and loss to follow up) therefore we will recruit N=160. With an average of 25-30 new cases per month from the sources outlined above, 60% consent rate, and 12 months recruitment, it is feasible to attain this sample of youth.

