8. DESIGN

Phase 3 of this study has both quantitative and qualitative components. The aims of the qualitative components of the study are to determine if participants liked using The App, and if their experiences of using it helped their recovery from concussion. In addition, qualitative data will be used to review any improvement suggestions to The App before commercialization. Using both qualitative and quantitative research methods we will explore

the usability of The Back2Play App components under consideration for the final version of the App to be commercialized.

Primary Research Outcomes

To assess:

- Risk for repeat head injuries within three months of study completion (3-6 months after injury)
- Duration of symptoms: Time to symptom resolution from date of injury

Secondary Research Outcomes

To assess:

- 1) The frequency of symptoms using PCSS.
- 2) Time to return to activity and time to progress through the 6 stages of RTA
- 3) Perceptions of the platform by parents and youth.
- 4) Accuracy of the algorithm embedded in the background of The App classifying the participant's stage of recovery

Measures

Symptoms

Concussion symptoms will be assessed on The Back2Play App for those randomized to The App group and via REDCap for those randomized to Usual Care. A modified version of the PCSS (consisting of 22 symptoms) will be completed by youth in both groups. The Likert scale was modified to detect the presence of symptoms rather than symptom severity. Symptom data will be collected 3x/day for participants using The Back2Play App and every 24 hours for participants in the Usual Care group.

Cognitive Activity

Cognitive activity will be assessed using a modified version of the scale developed by Brown et al. Participants in both groups will be asked to complete this scale once per day through REDCAP which will appear as follows:

"Please rate 1-5 what you've been doing today"

- 1- None- No reading, homework, text messaging or screen time (T.V., cell phone), can talk on phone
- 2- Minimal- 15 minutes of screen time or schoolwork 2x daily. Socialize with 1-2 friends, no longer than 30 minutes,
- 3- Moderate- Homework in 15 minutes blocks for a maximum of 45 minutes. Screen time/T. V in 15-minute blocks, for up to an hour daily.
- 4- High- Complete as much homework as tolerated. 1 test/week or tests with accommodation (i.e. longer time to write), less reading, homework and screen time than normal
- 5- Full- no restrictions to cognitive activity

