9.5. DATA ANALYSIS PLAN

The recordings of online consent (Zoom), for Phase 3, will be stored on a study computer and saved to a secure password encrypted server. As described above, participants will be asked to complete the (SUS). The SUS yields a single number representing a composite measure of the overall usability of the system being studied. Adjustments and modifications to The Back2Play App will be made before commercializing the product.

We will collect and report descriptively all demographic information, injury-related data (type, mechanism of injury, numbers of injuries), youth premorbid health history. Descriptive statistics such as means, medians, and frequencies will be reported where appropriate. Baseline comparisons will be performed between those that use The App and those whose recovery involved Usual Care with variables of mechanism of injury, age, sex, school performance and concussion history. These variables will be-analyzed using Pearson Chi Squared Cross Tabulations, T-Test and ANCOVA, to ensure the groups are similar. We will also evaluate agreement of the algorithm with the self-reported stage of recovery participants input using these same statistics.

The dichotomous variable, repeat injuries (coded as yes or no), will be analyzed using multivariate logistic regression and resulting odds ratios to determine if using The Back2Play App decreases risk of repeat injury. Confounders of age, gender, number of symptoms, time since last injury and comorbidities of premorbid mental health issues or learning disabilities will be examined as to their potential impact on outcomes. Many of these variables will be correlated with each other and these correlations will need to be examined carefully before they are entered into the analyses.

Time to symptom resolution will be analyzed using survival curves with Multivariate Cox regression analysis. Cox regression (also called proportional hazard models) is a method of survival analysis that models the time until some event as a function of either continuous or categorical predictors, allowing for the fact that not all subjects will experience the events of interest and that they will occur at different times.

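### The 0.8 power belongs to falls of 14 and 24 points in repeat head injury, not to the 10% effects called clinically significant, and time to symptom resolution has no sample size calculation

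*Combined protocol and SAP*

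**What the plan says.** The sample size paragraph in section 3 (Methods, Description of Population and Sample) opens with the effects that matter to the investigators: "A clinically significant effect of 10% decrease in repeat head injury and 10% decrease in recovery time would be of interest". The next sentence says that the calculation used "two sided significance of 0.05 and a power of 0.8 and based on our primary outcome of repeat head injury", a binomial variable. Two pairs of rates follow, each with its total:

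- "16% rate common in the literature" against "our anticipated 2% rate with adherence to protocols (from previous B2P study) N=128"
- "37% rate from concussion clinic at MCH" against "13% rate of our pilot data N=100"

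The larger total is taken and raised for 20% refusal and loss, giving 160 to recruit.

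Section 8 (Design) lists a second primary outcome: "Duration of symptoms: Time to symptom resolution from date of injury". Section 9.5 (Data Analysis Plan) gives its analysis: "Time to symptom resolution will be analyzed using survival curves with Multivariate Cox regression analysis". Repeat injury is to be analysed there by logistic regression with odds ratios. Neither section gives an event count, a hazard ratio, a median or a power for recovery time.

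**The concern.** The paragraph names one size of effect as clinically significant and then attaches its power to much larger ones. A fall from 16% to 2% is 14 points (14/16 = 88% relative). A fall from 37% to 13% is 24 points (24/37 = 65% relative). Neither is a 10% effect on an absolute or a relative reading, and the text does not tell the reader that 0.8 excludes the effect just named. For recovery time a 10% effect is named and nothing is calculated.

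What is at stake is how a non-significant result is read. Someone who takes 0.8 as the chance of detecting the effect called clinically significant may treat non-significance as evidence that the App gives no worthwhile benefit. The plan has no rule against that reading. Its planned summaries, an odds ratio and a hazard ratio, do not by themselves show whether a 10-point fall or a 10% shorter recovery has been excluded.

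**Working it through.** **Inputs.** From section 3: two-sided 0.05, power 0.8, rates 16% and 2%, rates 37% and 13%, totals 128 and 100, 20% refusal and loss, 160 recruited. From section 6: a 50% chance of either group, hence 1:1 allocation. Normal quantiles are 1.960 and 0.842.

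**Formula.** With d = p1 − p2 and p̄ = (p1 + p2)/2, let A = 1.960·√[2p̄(1−p̄)] and B = √[p1(1−p1) + p2(1−p2)]. Then n per arm = (A + 0.842·B)²/d², and power in the App's favour = Φ[(√n·d − A)/B].

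**Step 1: reproduce the plan's totals.**

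- 16% against 2%: A = 0.793, B = 0.392, n = (0.793 + 0.330)²/0.14² = 64.4 per arm, or 128.8 in total (stated 128).
- 37% against 13%: A = 1.200, B = 0.588, n = (1.200 + 0.495)²/0.24² = 49.9 per arm, or 99.8 in total (stated 100).
- 128/(1 − 0.20) = 160, as stated.

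The totals agree apart from rounding, which identifies the falls to which 0.8 applies.

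**Step 2: power at 64 per arm (128 evaluable).** Here √64 = 8.

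| Fall | d | A | B | Power |
|---|---|---|---|---|
| 16% to 2% | 0.14 | 0.793 | 0.392 | 0.80 |
| 37% to 13% | 0.24 | 1.200 | 0.588 | 0.89 |
| 16% to 6% (10 points) | 0.10 | 0.867 | 0.437 | 0.44 |
| 37% to 27% (10 points) | 0.10 | 1.293 | 0.656 | 0.23 |
| 16% to 14.4% (10% relative) | 0.016 | 0.995 | 0.508 | 0.04 |
| 37% to 33.3% (10% relative) | 0.037 | 1.323 | 0.675 | 0.06 |

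For example, 16% to 6% gives (8 × 0.10 − 0.867)/0.437 = −0.154, and Φ(−0.154) = 0.44. If the App truly lowered repeat injury by 10 points, about 56% of such trials from 16% and 77% from 37% would miss significance.

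**Step 3: sensitivity.**

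- All 160 evaluable (80 per arm): 52% for 16% to 6% and 27% for 37% to 27%.
- Fisher's exact test at 64 per arm: 34% and 17% for the 10-point falls, against 74% for 16% to 2% and 85% for 37% to 13%.
- Size needed for 0.8: 16% to 6% needs (0.867 + 0.368)²/0.01 = 152.5, so 153 per arm and 306 evaluable. 37% to 27% needs (1.293 + 0.552)²/0.01 = 340.4, so 341 per arm and 682 evaluable.

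**Step 4: recovery time.** There is nothing to reproduce. A power for a 10% shorter recovery would need an expected number of resolutions and a form for the time distribution, and the plan states neither as a design assumption.

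**The case against.** The best defence is that the paragraph hides nothing. Each pair of rates stands beside its own total, directly after the 0.8, and the 2% is called anticipated. Sizing a trial on an anticipated effect is a recognised choice, and an effect described as being of interest is not thereby declared the design effect. The introduction also labels Phase 3 a feasibility trial.

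Much of this stands. A careful reader can work out what was powered, and for that reason the point is one that should be fixed and not a fatal flaw. The feasibility label helps less: the Phase 3 description in the introduction sets an effectiveness comparison as its goal, and section 9.5 uses the regression to decide whether the App lowers the risk of repeat injury.

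Four stronger readings are tempting and are not supported:

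- *The sample size is miscalculated.* It is not; both totals and the 160 reproduce.
- *A 10-point fall always has less than half the power claimed.* The 44% and 23% belong to the two comparison rates in section 3. Lower control rates give more: an assumed 11% to 1% would have 67% at 64 per arm.
- *A null result could not exclude a 10-point benefit.* Whether it does depends on the interval observed. Non-significance alone does not settle it either way.
- *The trial has a known low power for recovery time.* Any such figure rests on a time distribution and event numbers that the plan does not supply. What the documents support is that no calculation is given.

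**Conclusion.** The point holds as a mismatch between the effect named as clinically significant and the effects that were powered. At 128 evaluable, the stated 0.8 becomes about 44% (from 16%) or 23% (from 37%) for a 10-point fall in repeat head injury, and about 4% or 6% for a 10% relative fall. Time to symptom resolution, though primary, was not sized.

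The figures assume 1:1 allocation, a pooled two-proportion z test, two-sided 0.05, and the whole 20% taken as loss after enrolment. If part of that 20% is refusal before randomization, the evaluable number lies between 128 and 160 and power lies between the two sets of figures given. Taking 10% as percentage points is the reading kinder to the plan. The power of the planned adjusted logistic model was not evaluated.

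**What to change.** Keep N=160. In section 3, state whether each 10% is absolute or relative, and replace the power statement with:

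> With 128 evaluable participants (160 less 20%), pooled two-proportion z test, two-sided 0.05, power is about 0.8 for a fall in repeat head injury from 16% to 2% and about 0.89 for 37% to 13%. The trial is not powered at 0.8 for a 10% effect: power for a 10-point absolute fall is about 44% from 16% and 23% from 37%. The trial was not sized for time to symptom resolution.

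If 10% is meant as relative, give about 4% and 6% in place of the 10-point figures.

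In section 9.5, report the risk difference for repeat injury with its 95% confidence interval beside the odds ratio. Report the difference or ratio in median time to resolution with its 95% confidence interval beside the hazard ratio. State that whether a 10% benefit is excluded will be judged from those intervals and not from non-significance alone. Without these two estimates that rule could not be applied, because the odds ratio and hazard ratio are on other scales.

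Cost: recruitment and study procedures do not change. The stated power becomes less favourable, and two estimates are added to the analysis.

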4. INCLUSION AND EXCLUSION CRITERIA

Inclusion Criteria

Youth aged 10-18 at the time of injury will be included in this proposal. Youth must have had an impact to the head or body and diagnosed with a concussion by a physician. The youth must be symptomatic on admission to the study, and be within the first month of their initial injury. In addition, youth and their parents/guardians must be able to understand and complete questionnaires in English or French.

Exclusion criteria: Youth will be excluded from the study if they 1) have a confirmed significant brain injury requiring resuscitation, 2) were admitted to the pediatric critical care unit or surgical intervention, and 3) if they suffered a concussion but are no longer symptomatic, 4) they have been admitted to the PICU and 5) have been diagnosed with a developmental disability.

5. HOW SUBJECTS WILL BE RECRUITED

For Phase 3 of the Back2Play App Development, youth from McMaster Children's Hospital and Montreal Children's Hospital will be recruited. Both McMaster Children's Hospital and Montreal Children's Hospital have Research Assistants on staff that will ask if potential recruits would like to hear more about the study. A study information letter will be provided to those who are interested. Consent and randomization can occur in the ED with Research Assistants using an online randomization system (https://www.random.org/lists/). If parents want time to consider whether they wish to participate, the overview of the details of the project with the Research Coordinator's contact information will be sent home with them. If later interested, they can contact the Research Co-ordinator who will arrange a time to review

the consent and possible assent form. Forms outline the project details, explain what participation involves, and seek to obtain written consent/assent.

The randomization process will be shared with participants. They will be informed that, due to the nature of the project, they may or may not get to use The Back2Play App. If a youth is not provided with The Back2Play App, they will be provided the Usual Care. Usual care often includes guidelines or protocols to help youth safely return to activity and school.

Participants will also be recruited from HWCDS, concussion clinics and from our Knowledge Translation partners in the Hamilton and Burlington community. The incidence of concussion has been low to due COVID-19 provincial restrictions and so we must expand our recruitment efforts. Principles/Teachers as well as Coaches and Athletic trainers will be given information about The Back2Play App Study. If a youth with a diagnosed concussion is identified, the youth and their families will be provided a letter of information by their Principal/Teacher/Coach or Athletic trainer. This letter will encourage the youth and/or their family to contact the Research Coordinator about The Back2Play App Study. Alternatively, the Principal/Teacher/Coach or Athletic trainer will be provided a contact form (Appendix 1.4) to collect the contact information of the youth their family so that the Research Team can contact the interested participants directly. Only youth/their families who consent to provide their information to their Principal/Teacher/Coach or Athletic trainer will be contacted directly using the Phone/E-mail script, whichever they prefer.

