6. PROCEDURES

* COVID-19 restrictions, if applicable: All interactions for the RCT with research staff will adhere to McMaster University's COVID-19 guidelines as well as government recommendations/protocols. As such, participants will be provided a combination of In Person/Zoom visits. Consent will most often be in person at the hospitals with research staff but if participants from the community choose to review consent over Zoom, they will be asked to sign consents through REDCap during the meeting. Zoom is an externally hosted cloud-based service (https://zoom.us/privacy-and-legal). Participants will be informed of the small risk of a privacy breach for data collected on Zoom. Participants will then be encouraged to express their concerns about using Zoom and be offered the alternative opportunity to participate via phone. An electronic copy of the consent or assent forms will be signed by participants on REDCap.

At the consent visit, regardless of method and site, participants will be fully informed of the protocol for each arm of the study (Usual Care and App group). Participants will also be informed of their chance (50%) of being assigned to either group. Due to the nature of the study participants and researchers are unable to be blinded to their study condition. Once consent is obtained, participants will be randomized to The Usual Care or The App group using computer generated codes. Those in The App group may be given their devices at the ED. Alternatively, if they can't stay for this they can come into The Institute for Applied Health Sciences (IAHS) within 2 days of consent to receive devices and download the App. If a participant is out of reasonable range to visit, devices may be mailed to them via FedEx within 1 day of providing consent and a Zoom meeting arranged to help download The App. If participants do not have an

iPhone above version 6, they will be provided an iPhone and an Apple Watch. They may choose to use their own iPhone if they have one with the appropriate model number. Participants will be informed that all devices supplied must be returned at the end of the study period.

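### Recruiting Research Assistants may also randomise in the ED with a public list tool, and no independent list holder, locked log, blocking or site stratification is described for this unblinded trial

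*Combined protocol and SAP*

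**What the plan says.** - **Who recruits.** Section 5 says that the two children's hospitals "have Research Assistants on staff that will ask if potential recruits would like to hear more about the study".
- **Who randomises, and with what.** The same section continues: "Consent and randomization can occur in the ED with Research Assistants using an online randomization system", and gives the address of a public website's list page. The statement covers the ED and is permissive. Families who want time, and many school and community recruits, deal with the Research Coordinator or the research team. The protocol does not say who randomises them.
- **When and how.** Section 6 says: "Once consent is obtained, participants will be randomized to The Usual Care or The App group using computer generated codes". It does not link these codes to the list tool or say who holds them. The ratio is 1:1: "Participants will also be informed of their chance (50%) of being assigned to either group".
- **Blinding.** Section 6 states that "participants and researchers are unable to be blinded to their study condition".
- **Outcomes.** Section 8 has two primary outcomes, repeat head injury and time to symptom resolution. The first comes from questions put to participants, the second from a symptom checklist that the youth complete.
- **Sources.** Section 3 lists a sports clinic, two hospitals, a school board and community physicians, whose youth "will be randomly assigned to the intervention or control groups". No stratification factor is named.
- **Analysis.** Section 9.5 lists age, gender, number of symptoms, time since last injury and comorbidities as confounders to examine. Site is not among them.

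**The concern.** When nobody is blinded and the participant reports the outcome, the recruiter's inability to foresee or alter the next assignment is the main protection against selection bias. Here the staff who decide whom to approach may also operate the randomiser, and no safeguard separates the two roles. A recruiter who expects a particular youth to do well with the App, or to struggle with the watch and three surveys a day, could act on that impression. Nobody would be able to tell afterwards.

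Site is a second, smaller issue. Section 7 leaves Usual Care to whatever guideline each practice follows, and the reinjury rates in section 3 differ by setting (37% at the hospital's concussion clinic, 16% in the literature). A chance imbalance within a site would mix local practice with the App effect in that trial's estimate.

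**Working it through.** **1. The plan's own figures.** Inputs from section 3: 16% vs 2%, two-sided 0.05, power 0.80. With pooled variance and mean rate 0.09:

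n per arm = [1.960·√(2·0.09·0.91) + 0.842·√(0.16·0.84 + 0.02·0.98)]² / 0.14² = (0.793 + 0.330)² / 0.0196 ≈ 64.4, so 65 per arm, or 130 in total.

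The plan states 128 (power 0.797 at 64 per arm), and 128/(1 − 0.20) = 160. The sample size reproduces and is not in dispute. Unequal arms barely matter for power: it is 0.81 at 54:74.

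**2. What the stated mechanism allows.** Two readings fit the text.
- *A full list is made in advance and held by the recruiter.* Upcoming arms are visible, and the order of approach or the decision to approach can follow them.
- *The tool is run once per youth after consent.* The next arm cannot be foreseen, but an unwelcome result can be re-run or discarded, and nothing records it.

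Neither reading includes a lock, a log or a separate list holder. Sections 5, 6 and 9.5, where these would appear, are present in the document.

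**3. Size if steering occurred (illustration).** All of these inputs are assumptions: 128 youth, no true App effect, and half the youth recovering at half the hazard of the rest. A fraction s of assignments sends good-prognosis youth to the App and the others to Usual Care. The remainder are coin tosses. The expected share of good-prognosis youth is then 0.5 + s/2 on the App and 0.5 − s/2 on Usual Care, so 60% vs 40% at s = 0.20. At that level 128 × 0.20 ≈ 26 youth are steered, and about half of them (13) land in a different arm from the one a coin would have given.

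Repeated runs of 1,000 to 4,000 null trials per setting, with an unadjusted Cox model, agree closely:

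| Steered | Null hazard ratio (App vs Usual Care, recovery) | Type I error |
|---|---|---|
| 0% | 1.00 | about 5% |
| 10% | about 1.07 | 5–7% |
| 20% | 1.13–1.16 | about 11% |
| 30% | 1.21–1.24 | 18–19% |

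Censoring at 90 days changes little (1.15 and 12% at 20% steering; 1.22 and 18% at 30%). When the prognostic factor used for steering is in the model, the hazard ratio is 1.00 and the error 5–6% at every level.

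**4. Repeat injury.** On the planning rates, 64 × 0.16 ≈ 10.2 and 64 × 0.02 ≈ 1.3 reinjuries are expected, about 12 in all. With so few events, moving a handful of youth could change the result.

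**5. Site.** The documents give no site sizes and no randomisation scheme. Assume simple 1:1 randomisation and a site of 40. The exact binomial then gives an 8.1% chance of a 26:14 split or worse and a 27% chance of 24:16 or worse. For a site of 20, a split of 13:7 or worse has a 26% chance.

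**The case against.** - **Allocation is not shown to be open.** A reader might infer from section 5 that assignments are unconcealed. The documents do not say so. Section 6 places randomisation after consent, and if the tool is run once at that point the next arm cannot be known beforehand. This stands: the defect is the absence of a described safeguard, not proven open allocation.
- **The Research Assistants are not shown to randomise everyone.** Their role is stated for the ED only, as something that can happen there, and the sentence names a staff group rather than one person doing both jobs. This also stands. Equally, the other routes have no named randomiser at all.
- **The error inflation is not that of the planned analysis.** The steering rates and the prognostic subgroup are assumed, and the model is unadjusted. Section 9.5 plans a multivariable Cox model, and much of what a recruiter can see overlaps its list of confounders. This largely stands. However, that list is given with the logistic model, and no adjustment removes steering on impressions that were never measured.
- **Simple randomisation is valid.** Chance imbalance by site adds variance, not bias, and the test's error rate already covers it. This stands, so stratification is a cheap gain in comparability rather than the repair of an error. With about 12 reinjuries expected, extra site terms in the logistic model also carry a real risk of overfitting.

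**Conclusion.** The point holds in a limited form. Recruiting staff may randomise in the ED with a public list tool, and the plan describes no independent list holder, locked or logged system, blocking or stratification by site. The trial is unblinded with self-reported primary outcomes, so under either reading of the mechanism selection bias is not prevented.

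The likely size is unknown, because the documents give no basis for a steering rate. The unadjusted illustration runs from almost nothing at 10% steering to a null hazard ratio of 1.21–1.24 and 18–19% type I error at 30%. Where the relevant prognosis is measured and modelled, the distortion falls towards zero. These figures should not be read as the error rate of the planned analysis, and the text does not support saying that allocation is in fact open or that site was deliberately ignored. The sample size is unaffected. The change is worth making because it is cheap and cannot be made after enrolment. If safeguards already exist, stating them would settle the concealment part.

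**What to change.** 1. **Allocation (sections 5 and 6).** Replace the list tool with an allocation list prepared by someone who does not recruit, in random permuted blocks stratified by site, with small sources pooled. Keep block sizes varied and undisclosed: with a fixed block of four, an observer who always guesses the arm that is behind is right about 71% of the time.
2. **Concealment.** Lock the list in the REDCap system that the trial already uses. Let it reveal each arm, with user and time logged, only after eligibility and consent are recorded.
3. **Coverage.** Apply this to every route: ED, later contact with the coordinator, school and community. Say who carries out the step on each.
4. **Analysis (section 9.5).** Stratify the Cox model by the same pooled site groups. Keep a site term in the logistic model optional, because few reinjuries are expected.

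**Cost.** A one-time set-up, wording changes in three sections, and REDCap access for staff at the point of consent. Pooling small sources gives up some balance within each of them.
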